The Research Staff will keep the paper records of the following: Informed Consent, Documentation of Informed Consent Form, Visits Chart, Completed Research Subject Profile and Data Collection Flowsheet Form on each subject who met the inclusion/exclusion criteria and were randomized into one of the treatment groups in a locked filing cabinet in Florida Hospital. The study coordinator will keep all paper records of Review Preparatory for Research Masterlist, Inclusion/Exclusion Form, Research Subject Database and Florida Hospital Study Coordinator Data Collection Flowsheet in a locked filing cabinet in Florida Hospital and store the electronic records of Review Preparatory for Research Masterlist and Research Subject Database in a password protected Florida Hospital computer until data collection is completed. Once data collection in a research site is complete, the study coordinator will collect all paper forms personally from the Research Staff. The study coordinator will forward all paper and electronic records to the principal investigator, and delete all electronic records from his secured computer. The principal investigator will complete the following electronic excel templates for data analysis: Clinical and Sociodemographic Characteristics at baseline_FL Hospital; Clinical and Sociodemographic Characteristics at baseline_Outside Fl Hospital; Timed Up and Go Test-Retest; IPAQ Admission, Discharge and 4-weeks; TUG, DGI, mCTSIB and DHI on Admission and Discharge; and Total Number of Visits, Length of Intervention, Step Log and Step Goal. The principal investigators will forward completed excel templates to the data analysts for statistical analysis by email. The principal investigator will keep all electronic regards in a secured Florida Hospital computer and all paper records in a locked filing cabinet in Florida Hospital for seven years after the research study has been closed. After that period of time, all paper records will be shredded and electronic records will be deleted in the computer.

Data Quality

N/A

Data Sharing (outside of Florida Hospital)

The principal investigator may share the research data with accreditation organizations and regulatory agencies, dissertation committee, and publications, medical meetings, or scientific journals for the purposes of completing the research study, and analyzing and evaluating the results. Individual patients (subjects) will not be identified during data sharing, and a research number will be used instead during the data sharing process, unless necessary to carry out the research study or required by law.

Sample Size Determination

A priori power analysis predicting a large effect size ($F=.25$) determined that a total of 54 subjects (18 in each group), who met the inclusion and exclusion criteria will be needed, with alpha at the conventional value of .05 to achieve a .80 power, that includes an assumption of a dropout rate of 10% .

Statistical Analysis Plan

The results will be presented through the following tables with supporting explanations:

- Clinical and sociodemographic characteristics of participants by group at baseline.
- Comparisons of TUG, DGI, mCTSIB and DHI between the three intervention groups on admission and discharge.
- Comparisons of self-reported walking activity (walking MET-min/week) and total self-reported energy expenditure (total physical activity MET-min/week) as determined from the IPAQ short form on admission, discharge and four-week follow-up between the three intervention groups
- Comparisons of averages of compliance to step log recording and compliance rate for meeting step goal between the VRWP and VRW groups. Compliance is defined as low (<33%), moderate (33%-75%) and high (>75%) based on the step log or walking log. This grading of compliance was used by Hall and colleagues in their research on efficacy of gaze stability exercises in older adults with dizziness.⁵³
- Comparisons of total number of visits and length of interventions in weeks between the three intervention group.
- Intraclass Correlation Coefficients for the Timed Up and Go test-retest reliability
- Result of stepwise linear regression analysis for TUG, DGI, mCTSIB and DHI

All interval and ratio data will be tested for normality prior to undertaking the data analysis. Descriptive statistics will be used to describe the characteristics of the sample and compare the three groups at baseline. This will include Analysis of Variance (ANOVA) for parametric and Chi Square for nonparametric sociodemographic and clinical data.

Analyses will employ five repeated measures Analysis of Covariance (ANCOVA), adjusting for age, with two independent variables (group and time) and five outcome measures (TUG, DGI, DHI, mCTSIB and IPAQ short form). The adjustment of age is based on age-related decline. Intraclass Correlation Coefficient will be calculated to establish the test-retest reliability of the TUG and a stepwise linear regression with age as covariate will be conducted for all 54 subjects at baseline to determine if TUG, mCTSIB and DGI are predictors of DHI. Two-tailed test will be utilized to compare the compliance with step log recording and meeting step goals between the two walking groups (VRWP and VRW), and ANOVA to compare of total number of visits and total length of intervention in weeks between the three groups. Alpha for all analyses will be set at 0.05 to test for significant difference.

Potential Risks and Benefits

Potential Benefits

Possible benefits include improved physical function.

Potential Risks

The addition of a prescribed walking program in the treatment of dizziness will challenge the subject's balance, and in rare cases may result in falls or more dizziness.

Performance-based outcomes such as mCTSIB, DGI, and TUG check for the subject's reaction whenever in a condition of unsteadiness. The risks associated with these tests are the potential for falls and for dizziness. Self-report questionnaires such as the DHI and IPAQ will need the subject to read the questions and recall past experiences. Looking down and reading the questions may provoke dizziness and eye strain. Other possible risks for subjects are: 1) finding the questions to be sensitive 2) emotional discomfort (uncomfortable/embarrassed/sad/tired) and 3) distress as subject thinks of experiences.

Mitigation of Risks

The research staff (treating physical therapist) will supervise the treatment at all times to minimize any such risks.

Provisions to Protect the Privacy Interest of Subjects

Subjects will be assigned research numbers for study-related records and data sharing. The patient's confidentiality will be protected by observing the HIPAA policies and procedures.

Early Withdrawal of Subjects

Investigator Withdrawal of Subjects

The PI may terminate the participation of the subject in the study if the subject may be in any danger or no longer meets the inclusion criteria of the study.

Subject Request for Withdrawal from Study

Subjects may withdraw or take away the permission to use and disclose their health information for any reasons at any time. This can be done by sending a written notice to the PI. Information that has already been gathered may still be used or given to others, however no new health information that might identify the subject will be gathered after the subject withdraw from the study.

Data Collection and Follow-up for Withdrawn Subjects

Patients who request withdrawal or who are withdrawn by the PI from the study will have their information that has already been gathered and shared in the research database. These data will be included in the data analysis. The percentage of patients withdrawing will be calculated.

Adverse Event Reporting

At each therapy visit of the subject, the research staff/treating therapist will seek information if there is any adverse event caused by taking part in the study. In the event of a research-related injury, the subject should report this in person or by phone to the research staff/treating therapist and PI. All adverse events will be reported to Florida Hospital's IRB and Nova Southeastern University's IRB following their respective policies for reporting adverse events.

Safety Monitoring Plan

Safety Monitoring
N/A

Data and Safety Monitoring Board (DSMB) or Equivalent
N/A

Ethical Considerations

Subjects in the VRW and VR group will receive a pedometer after they completed the study.

Sharing of Results with Subjects

Results of the study that are part of standard physical therapy will be shared with subjects and referring physicians. Letters will be sent to all participants that contain the results of the research once the research is completed.

Funding Source

Application for funding will be done through the Adventist University in January 2018. The principal investigator is currently requesting managers to allow the allocation of her Continuing Education budget for 2018 for this study.

Subject Stipends or Payments

The pedometer will be donated to the 54 participants, who met the inclusion and exclusion criteria and randomized into one of the three treatment groups, as a reward for participating in the research study and for them to perpetuate their physical activity.

Publication Plan

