There are four purposes to this study. The primary purpose of this study is to evaluate the impact of walking as an exercise component of VR on both primary and secondary vestibular-specific outcome measures. The primary outcomes are mCTSIB, TUG test, DGI, and DHI, while the secondary outcomes are the total number of visits and length of interventions (in weeks). The second purpose is to evaluate whether pedometers increase the adherence of older adults with vestibular issues to a walking program. This will be measured by change in physical activity, as represented by International Physical Activity Questionnaire (IPAQ) Walking Metabolic Equivalent of Task (MET)-minutes/week and IPAQ Total Physical Activity MET-minutes/week scores from the IPAQ short form during the episode of care (admission and discharge) and on four-weeks follow-up compared to those patients who only received instructions to walk without a pedometer. The third purpose of this study is to establish test-retest reliability of the TUG test on older adults with dizziness. Lastly, the fourth purpose of this study to investigate if the TUG, DGI, and mCTSIB are significant and strong predictors of the DHI in older adults with dizziness. Protocol #1365169 “Predictors of Disability in the Older Adults” is being performed to supplement the number of subjects for the fourth objective of this study.

Study Design

Research Design

1. Experimental Design. To answer the first and second study objectives, a pragmatic, randomized, prospective, clinical study on 54 older adults with dizziness will be utilized. This will be conducted at Florida Hospital Sports Medicine and Rehabilitation locations that offer vestibular therapy. These are in East Orlando and Winter Park.
2. Correlation Design. A correlation analysis will be performed on the data collected on 54 subjects in the experimental design to establish the test-retest reliability of the Timed Up and Go.
3. Cross-sectional Descriptive Design. A regression analysis will be performed on three predictors of the Dizziness Handicap Inventory, obtained from the data collected on 54 subjects in the experimental design and from Florida Hospital Sports Medicine and Rehabilitation Physical Therapy medical charts from June 2015 to June 2018 that met the inclusion and exclusion criteria that were outlined in the Protocol #1365169.

Study Agent, Device, and/or Intervention Description

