1. Age 65 years or older referred for physical therapy evaluation for symptoms of dizziness, postural instability, or both
2. Able to walk without the physical help of another person, with or with no assistive device
3. Able to follow commands and execute the examination and intervention instructions in the English language
4. Willing to participate in a phone interview four weeks after discharge
5. Able to provide informed consent

Exclusion Criteria

1. Unstable medical issues, such as unstable or uncontrolled cardiovascular conditions, elevated blood pressure (Systolic greater than or equal to 140mmHg and diastolic greater than or equal to 90mmHg), orthostatic hypotension (a fall in systolic blood pressure of at least 20mmHg or diastolic blood pressure of at least 10mmHg when a person stands from a sitting or lying down position), uncontrolled metabolic disease, as determined by the evaluating physical therapist, documented in the Functional Comorbidity Index, vital signs and assessment portion of the initial evaluation.
2. History of falls from syncopal origin
3. Dizziness of central origin, such as stroke, head injuries, MS or PD;
4. Active BPPV (patients with positive dix hallpike and/or roll test)
5. Inability to walk without physical assistance.

Resources Available

Each site will have research staff (treating physical therapists). Prior to enrollment of subjects, training of the study coordinator and research staff will be conducted onsite or online by the principal investigator. This training will cover the following: multi-site communication, subject recruitment, informed consent, inclusion and exclusion criteria and data collection. Research staff will receive instructions on randomization, interventions, outcome measures, and the use of Fitbit Zip pedometer. To establish interrater reliability, participating therapists will rate the DGI, mCTSIB and TUG by watching a video of a volunteer patient, and the DHI and IPAQ short form sample

questionnaires. To ensure compliance with the outcome measure equipment, research staff will sign a Research Equipment Compliance Document. The principal investigator will conduct inspection of equipment in each site, co-sign the document and keep the paper record in a locked filing cabinet in Florida Hospital.

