The Bland-Altman plots show the distribution of the difference scores of two measurements around zero. The 95% level of agreement means that 95% of the difference scores fall within two standard deviations above or below the mean of the difference scores. Values closer to zero means greater reproducibility between two repeated measures.

Objective 4. To investigate if the TUG, DGI, and mCTSIB are significant and strong predictors of the DHI in older adults with dizziness.

The subjects were then grouped based on the DHI test results, using the categories suggested by Whitney et al: 0-30 for mild, 31-60 for moderate, and 61-100 for severe.¹⁰⁴ This analysis is similar to the work of Vereeck et al⁸⁴ to obtain a better picture between the dependent variable DHI and the independent variables: mCTSIB, TUG, and DGI. Kruskal-Wallis analysis was calculated to compare group means for age, mCTSIB, TUG, and DGI. The significance values were adjusted by the Bonferroni correction for multiple tests.

Before the multiple linear regression analysis, assumptions were tested to establish the nature of the data. The obtained Durbin-Watson statistic for the analysis of the independence of

observations is 2.639. The Durbin-Watson statistic can range from 0 to 4, with a value of approximately 2 to indicate that there is no correlation between residuals. The obtained value is close to 2, therefore it can be accepted that there is the independence of observations. The assumptions of homoscedasticity, normality, and multicollinearity are upheld. There is no presence of outliers in the data.

The Spearman Rho correlation coefficients were calculated to establish the relationships between the DHI and mCTSIB, TUG and DGI. As a general guideline, the value 0.00 to .25 indicates little to no relationship, 0.25 to 0.50 suggests fair relationship, 0.50 to 0.75 denotes moderate to good relationship and above .75 is considered good to excellent relationship.⁴⁴ Then, a multiple linear regression analysis was conducted for a continuous dependent variable and three independent variables to identify the predictors of DHI.

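### Objective 4: the sections conflict on who is analysed, and the trial-plus-chart regression, if pooled, has no term for data source

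*Combined protocol and SAP*

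**What the plan says.** The Objective 4 regression is described in three places, and they do not match.

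- **Study Design, Research Design, item 3.** The predictor data are "obtained from the data collected on 54 subjects in the experimental design and from Florida Hospital Sports Medicine and Rehabilitation"; the text runs on to "Physical Therapy medical charts from June 2015 to June 2018", for patients "that met the inclusion and exclusion criteria that were outlined in the Protocol #1365169". Study Objectives gives the reason: the other protocol "is being performed to supplement the number of subjects for the fourth objective of this study".
- **Statistical Analysis Plan.** A stepwise regression, with age as the covariate, on the baseline data of the 54 trial subjects. Chart patients are not mentioned.
- **Data Analysis, Objective 4.** Here "a multiple linear regression analysis was conducted for a continuous dependent variable and three independent variables to identify the predictors of DHI". No sample size is given and age is not listed.

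None of the three names a term for source, a comparison of the two sources, or a trial-only analysis.

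On how the sources arise, the Inclusion Criteria require informed consent and "Willing to participate in a phone interview four weeks after discharge". Resources Available states "Prior to enrollment of subjects, training of the study coordinator and research staff will be conducted onsite or online by the principal investigator", and adds "To establish interrater reliability, participating therapists will rate the DGI, mCTSIB and TUG by watching a video of a volunteer patient". The timeline under Study Duration puts training in December 2017 and enrolment from January to August 2018. Study Visits says that the trial's own baseline TUG, DGI, mCTSIB and DHI are routine-care scores that the study coordinator takes from the chart.

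**The concern.** Objective 4 asks whether a patient's TUG, DGI and mCTSIB predict that patient's DHI. If two groups of patients are stacked and the model cannot tell them apart, the slope combines the relation within each group with any gap between the groups. There are two reasons to think that a gap is possible. Consent and willingness to take a call could hardly have been applied to past charts. Much of the chart window also lies before the therapists were trained and rated a common video. A predictor could then look stronger or weaker than it is, or reach significance, because of where the record came from. Objective 4 is planned as a paper of its own, so nothing else in the trial would correct the result. Before any of this, a reader cannot tell which patients the regression covers.

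**Working it through.** **Analysis set.** Research Design and Study Objectives both point to pooling. The Statistical Analysis Plan section points to the 54 trial subjects alone. Data Analysis is silent, and nothing ranks the sections. Pooling is therefore planned but not settled. There is no Objective 4 figure to reproduce: the 54 in Sample Size Determination was set for the three-group comparison.

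**Calendar.** June to December 2015 is 7 months, 2016 is 12, and January to November 2017 is 11: 7 + 12 + 11 = 30 months before the training month. Adding December 2017 (1) and January to June 2018 (6) gives 37. The share is 30/37 = 81% of months. It is a share of patients only if charts accrue evenly, which the documents do not say.

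**Slope bias, one predictor.** Let DHI = a + β·DGI + δ·S, with S = 1 for a chart patient. Let p be the chart share, Δ the gap in mean DGI and σ the within-source SD of DGI. Leaving S out changes the expected slope from β to β + B, where

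B = δ·Δ·p(1−p) / (σ² + Δ²·p(1−p)).

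All inputs are assumptions, because the documents give neither the chart number nor any spread: σ = 4, p = 0.5, δ = 5 or 10, Δ = 1, 2 or 3.

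| Δ (DGI points) | B at δ = 10 | B at δ = 5 |
|---|---|---|
| 1 | 2.5/16.25 = 0.15 | 0.08 |
| 2 | 5/17 = 0.29 | 0.15 |
| 3 | 7.5/18.25 = 0.41 | 0.21 |

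Units are DHI points per DGI point. B takes the sign of δ·Δ, so it can steepen or flatten the slope.

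**What δ means.** It is the DHI difference between sources at the same DGI. The raw DHI gap is δ + β·Δ, and its second part is genuine prediction. Suppose β = −2, chart patients are 3 DGI points lower, and the raw gap is 10. Then 6 points are explained, δ = 4, and B = 4 × (−3) × 0.25/18.25 = −0.16. If the DGI gap explains the whole DHI gap, B = 0.

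**Recording shift in the predictor only.** If chart DGI is recorded Δ points off and DHI is unaffected, the slope becomes β·σ²/(σ² + Δ²·p(1−p)). The factors are 16/16.25, 16/17 and 16/18.25, a loss of about 2%, 6% and 12%. A slope of zero stays zero.

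**False prediction.** A simulation (2,000 runs per cell) fitted DHI on age, TUG, DGI and mCTSIB with no association within either source. It used 54 trial subjects plus 54, 108 or 200 chart patients. Entries are the share of runs in which the joint test of the three predictors had p < 0.05.

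| Shift between sources (SD units) | No source term | Source term |
|---|---|---|
| Predictors only or DHI only, 0.5 | 4–6% | 5–6% |
| Both 0.3 | 5–6% | 5–6% |
| Both 0.5 | 8–10% | 4–5% |
| Predictors 0.8, DHI 0.5 | 12–15% | 4–5% |
| Both 0.8 | 24–34% | 5% |

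Monte Carlo standard error at 5% is √(0.05 × 0.95/2000), about 0.5 percentage points.

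**The case against.** The strongest reply is that the premise may be absent. If the Statistical Analysis Plan section governs, no chart patient enters and there is nothing to adjust for. That stands, and it is why the analysis set must be settled first.

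Second, the criteria of Protocol #1365169 are not shown and could repeat the trial's clinical criteria. Both sources are routine physical therapy scores from one organisation, which narrows any gap. That also stands: a difference is plausible, not shown.

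Third, a reader might infer that testing before training could by itself make a useless test look predictive. The documents do not support this. The DHI is a self-report questionnaire with fixed item scores, so training should bear mainly on the three performance tests. A shift in the predictors alone attenuates a real slope and leaves the false-positive rate at about 5%.

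Fourth, the biases look small beside sampling error. With an assumed residual DHI SD of 20 and 108 patients, the standard error at Δ = 3 is 20/(√108 × √18.25) = 0.45, so even 0.41 is below one standard error. This is fair, but it does not make the bias harmless: 0.41/0.45 = 0.91 standard errors turns a two-sided 5% test into one that rejects with probability P(Z > 1.05) + P(Z < −2.87), about 15%. For a given mix of sources, adding charts shrinks the standard error and leaves the bias unchanged.

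Fifth, the Data Analysis section is in the past tense, so any change is now a re-analysis. That is correct and affects only how it is labelled.

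**Conclusion.** Two points hold. The sections contradict each other on the Objective 4 analysis set. If the sources are pooled as Research Design states, the model has no protection against a source difference. The bias arises only when DHI differs by source at fixed predictor values and a predictor's mean also differs. Under the stated assumptions it is 0.15 to 0.41 DHI points per DGI point for a 10-point shift, and half that for 5 points. It is negligible when both shifts are about 0.3 SD, material from 0.5 to 0.8 SD, and zero if the sources do not differ.

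Three stronger readings go beyond the documents. That pooling was certainly done is contradicted by the Statistical Analysis Plan section. That chart patients were clinically different cannot be judged without the other protocol's criteria. That most chart patients were tested before training is a count of calendar months, not of patients. This is a correction worth making to a fourth, cross-sectional objective; it does not touch the randomised comparison.

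**What to change.** 1. Reconcile Research Design, Statistical Analysis Plan and Data Analysis on the Objective 4 analysis set. Give the number from each source, both sets of eligibility criteria and the covariates. State also that no trial subject is counted again through a chart from January to June 2018, where the chart window overlaps enrolment; the other protocol may already ensure this.
2. If the sources are pooled, add a trial-versus-chart indicator and make that model the main estimate. An indicator for before or after training is not a substitute, because 7 of the 37 chart months fall in or after December 2017.
3. Report the trial-only estimate beside it as a sensitivity analysis. Do not make the conclusion depend on the two agreeing: no criterion for agreement exists, and the charts were added because 54 subjects were thought too few.
4. Label the added analyses as post hoc where results already exist.

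The cost is one degree of freedom and one table row. The source of each record should already be known, so no new data are needed. If the analysis set is the 54 trial subjects alone, only item 1 applies.

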54 participants will receive vestibular rehabilitation as prescribed by the treating therapists. Vestibular Rehabilitation is composed of four different exercise components: gaze stability, habituation, balance training and general conditioning.²⁵ Two of the intervention groups will receive vestibular rehabilitation plus walking with and without pedometer while the third intervention group will be vestibular rehabilitation only.

Study Site(s)/Location(s) and Number of Subjects

Subjects will be recruited through consecutive admissions at participating Florida Hospital outpatient departments until the target total number of subjects who met the inclusion and exclusion criteria is achieved (n=54).

Florida Hospital site locations:

The research will be conducted at Florida Hospital Sports Medicine and Rehabilitation locations that offer vestibular therapy. These are in East Orlando and Winter Park. Estimated number of subjects in each location is 27 subjects who met the inclusion and exclusion criteria.

Name of external site(s) outside of Florida Hospital:

N/A

Total number of all sites:

Estimated number of subjects at all sites combined is 54.

Multi-Site Research Logistics/Communication Plan

To streamline communication among sites, the PI will communicate online or in person to all sites' research staff the following information once they are available and during the monthly meetings: most current version of the protocol and consent form, reportable new information, amendments, and study progress. All modifications must be communicated to sites, and approved before the modification is implemented. Electronic and paper research data will be submitted to the study coordinator. The study coordinator will keep all research data in a locked filing cabinet in Florida Hospital and all electronic data in a password protected Florida Hospital computer. The study coordinator will ensure that the study is conducted by the research staff appropriately and will report non-compliance with the study protocol or applicable requirements in accordance with local policy to the PI and IRB. Problem, interim results, and closure of the study will be communicated to the study coordinator and PI.

Research Conducted in a Foreign Country

N/A

Community-Based Participatory Research

N/A

Subject Selection

Vulnerable Populations (if applicable)

N/A

Inclusion Criteria

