Documentation of the informed consent process is required to establish that the subject was accurately and adequately informed and that no study-related procedures were initiated prior to obtaining informed consent. The research staff will complete the Documentation of Informed Consent Form (HRP-803) that contains the consent progress, date consent was obtained and that consent was obtained prior to initiating any research procedures. The research staff will explain the consent form to interested patients. A follow-up phone will be conducted by the principal investigator, research assistant or research staff to the potential participant prior to the beginning of the tenth visit. If the patient expressed willingness to take part in the research, the research staff will obtain a signature of subject during patient's visit/a face-to-face encounter with the patient. The study coordinator will perform a retrospective chart review on the subject's medical chart once a signed informed consent form is obtained.

Randomization

For the experimental design, block randomization will be performed to ensure

equal number of participants in each treatment group. The study coordinators will have a prerandomized masterlist of subjects generated using an online randomization program (<https://www.sealedenvelope.com/simple-randomiser/v1/lists>). The signed informed consent must be returned prior to tenth visit. Once the study coordinator confirmed that the subject is eligible to participate in the study by completing the Inclusion/Exclusion Form based on the retrospective chart review of the patient's medical record, he will assign the subject with an ID number and randomize the subject into one of the three groups as determined by the prerandomized master list: first intervention group (n=18, VR plus walking with pedometer, VRWP), second intervention group (n=18, VR plus walking instruction only, VRW) and control group (n=18, usual care, VR). The study coordinator will keep paper and electronic records that contain the list of research numbers with names of all the subjects, date of birth and medical record number.

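### Randomisation is not described as stratified by the two clinics and no analysis accounts for site, which costs some precision and interpretability at 18 per arm

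*Combined protocol and SAP*

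**What the plan says.** - **Sites.** The section Study Site(s)/Location(s) and Number of Subjects names two clinics ("These are in East Orlando and Winter Park") and adds: "Estimated number of subjects in each location is 27 subjects who met the inclusion and exclusion criteria".
- **Allocation.** Under Randomization, blocking has one stated purpose, equal arm sizes ("block randomization will be performed to ensure" that equality). The coordinator is to "randomize the subject into one of the three groups as determined by the prerandomized master list". Neither a stratification factor nor a block size is given.
- **Planned analysis.** The Statistical Analysis Plan specifies repeated-measures ANCOVAs "with two independent variables (group and time"), adjusted for age only. ANOVA is planned for number of visits and weeks of treatment.
- **Analysis in the Data Analysis section.** Normality was not met, so rank tests replace these. Kruskal-Wallis is used between groups, and Wilcoxon signed-rank and Friedman tests within groups. None has a stratum or covariate.
- **Staffing.** Each site has its own treating therapists (Resources Available). They prescribe the rehabilitation, deliver the walking intervention and collect the outcome scores, and the PI also treats.
- **Baseline data.** Site is not among the variables listed under Study Visits.

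**The concern.** Two clinics with different therapists may differ in how much their patients improve, how many visits they use and how many weeks they stay. The rehabilitation content is left to the therapist, so some difference is plausible. Blocking on a list that ignores site equalises the arm totals but not the site mix within each arm. At 18 per arm the mix can be visibly uneven by chance.

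Whatever the clinics do differently then adds noise to the arm contrast, and no planned analysis removes it. A reader who sees one arm drawn mostly from one clinic could not separate arm from clinic. Because site is not a listed baseline variable, the imbalance might not be reported at all.

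**Working it through.** **Inputs from the documents.** Two sites, 27 expected at each; three arms of 18. The totals agree: 2 × 27 = 54 = 3 × 18.

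The power calculation behind 54 cannot be reproduced, because the test, the number of time points and the within-subject correlation are not stated. The point takes 54 as given and does not depend on that calculation.

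**Assumption.** The site difference in improvement, d, is taken as 0.5 to 1.0 within-site SD. The documents give no figure.

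**1. How uneven can the site mix be?** If site is ignored, the number from one clinic in each arm follows a multivariate hypergeometric distribution (27 drawn from 18 + 18 + 18). Exact results:

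| Event | Probability |
|---|---|
| A given pair of arms differs by 4 or more at a site | 0.247 |
| Some pair of arms differs by 4 or more | 0.466 |
| Some pair differs by 6 or more | 0.155 |
| Some arm splits 12:6 or worse | 0.315 |
| Walking (36) and control (18) differ by 25 or more points in site share | 0.148 |

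Simulating one central list with subjects arriving in random site order gives 0.468, 0.463 and 0.465 for the second row, with blocks of 3, 6 and 9. Blocking without site therefore does not help. If the clinics recruited 36 and 18 instead (assumption), the second row is 0.43.

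**2. Typical imbalance, walking versus control.** Let k be the number of control subjects from one clinic.
- Var(k) = 18 × 0.5 × 0.5 × (54 − 18)/(54 − 1) = 3.057, so SD(k) = 1.748.
- The difference in site share is (27 − k)/36 − k/18 = 0.75 − k/12.
- Its SD is 1.748/12 = 0.146.

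**3. Shift in the contrast.** Shift = share difference × d.
- Typical (one SD of imbalance): 0.146 × 0.5 = 0.07 SD; 0.146 × 1.0 = 0.15 SD.
- At a 25-point imbalance, reached or exceeded about 15% of the time: 0.25 × 0.5 = 0.125 SD; 0.25 × 1.0 = 0.25 SD.
- Standard error of the contrast: √(1/36 + 1/18) = 0.289 SD.

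The typical shift is thus 0.073/0.289 = 25% to 0.146/0.289 = 50% of one standard error.

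**4. What this does to precision.** Averaged over allocations, the shift adds to the variance of the contrast: 0.0833 + (0.146 × d)².
- d = 0.5: √(0.0833 + 0.0053) = 0.298, about 3% above 0.289.
- d = 1.0: √(0.0833 + 0.0213) = 0.323, about 12% above 0.289.

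**5. With one list per clinic (27 each).** Blocks of 3 or 9 give exactly 9 per arm at each site. With blocks of 6, 27 = 4 × 6 + 3, and the largest gap is 2. The probability of a gap of 4 or more falls to 0.

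**The case against.** The case against is strong on several counts, and most of it stands as a limit on the size of the point.

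- **Bias.** A reader might infer that an uneven site mix biases the trial. It does not. Allocation is random, so the comparison is unbiased in expectation and the test stays valid. The loss is in precision and interpretability.
- **Scoring differences.** DGI, TUG, mCTSIB and DHI are compared as pretest-posttest differences or as group by time. A stable difference in how a clinic scores largely cancels, so only a site difference in improvement matters. Visits and weeks are not change scores, and for them this defence does not apply.
- **Discharge.** A reader might infer that therapists control visits and weeks because they decide discharge. No section says who decides discharge; the documents say only that therapists prescribe the rehabilitation and that visits and weeks are recorded.
- **A single list.** A reader might take it as established that one undivided list served both clinics. The text refers to a master list but also to coordinators in the plural, and does not say whether the list was split by site. Lack of stratification is read from silence.
- **Therapist effects.** Stratifying by site does not balance therapists within a clinic. Nor does it address the fact that the PI and other therapists both treat and score.
- **Mitigation.** Common training, a video-based rating exercise, equipment inspection and monthly meetings should narrow scoring and conduct differences. They do not standardise what is prescribed.
- **Predictability.** Therapists recruit and deliver treatment unblinded. Short blocks within a clinic are easier to guess than a list interleaved across two clinics, which is a real cost of stratifying.

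What survives is that site is a known, recorded grouping in a small trial and nothing in the described design or analysis uses it.

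**Conclusion.** The point holds as a minor one. No stratification by clinic is described, and no analysis accounts for site. An uneven mix is likely: about 47% for a gap of 4 or more between some pair of arms, and about 15% for a 25-point gap between walking and control. Its expected effect is modest. For an assumed site difference in improvement of 0.5 to 1.0 SD, the typical shift is 0.07 to 0.15 SD, within a standard error of 0.29 SD.

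The shift of 0.125 to 0.25 SD belongs to the 15% tail and should not be read as the usual case. All of these shifts scale with the assumed site difference; if the clinics improve alike, the cost is nil. The probabilities rest on the estimated 27 per site and on a list that ignores site. The therapist component cannot be sized, because the number of therapists is not given.

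**What to change.** - **If the list has not been used:** generate one permuted-block list per clinic, with varying block sizes concealed from the treating therapists, including the PI in that role. The Data Analysis section is written in the past tense, so this step may no longer be available.
- **Whether or not it has been used:** add site as a fixed factor in each ANCOVA, together with its interaction with time, because the arm effect is read from group by time.
- **Where rank tests are used:** Kruskal-Wallis takes no fixed factor, so a model term is not enough. Replace or supplement it with a site-stratified rank test. Van Elteren's test suits the pooled walking-versus-control comparison; use the corresponding stratified test for three groups.
- **Reporting:** give arm-by-site counts, the block size, and whether the list was divided by site.

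**Cost.** The total stays at 54. Arm totals may differ by one or two, and 9 per arm at each clinic is not guaranteed, since 27 is an estimate. Short per-clinic blocks are somewhat more predictable, hence the varying and concealed sizes. Site spends one degree of freedom, plus one per post-baseline time point for its interaction with time. Therapists within a clinic remain unbalanced.
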